9.3.3 Health-Related Quality of Life

9.3.3.1 Change in utility, based on EQ-5D-5L, up to Day 180

EQ-5D-5L will be analyzed by the index value, the overall QALY (Quality-Adjusted Life Years) at Day 30 and 180 (see Appendix 1 for details), and the VAS score.

The QALY scores will NOT be adjusted to e.g. a half yearly time scale at Day 180.

As the QALY is not defined for patients with all remaining values missing, and hence also not defined for those dead, the analyses will automatically only be analyzed for those surviving up until Day 30 and 180 respectively.

For patients with missing baseline index value, the QALY score will also be set to missing. For robustness, a sensitivity analyses will be performed, imputing the missing baseline scores with the overall mean of the baseline health index. Baseline is the timing prior to acute admission.

The QALY at Day 30 and 180 will be compared between treatment arms using an ANCOVA model with baseline health index as covariate, and treatment as factor. Estimated treatment differences (to placebo) along with a 95% confidence interval will be presented.

The index value and VAS scores will be analysed separately for survivors and non-survivors at Day 180 (since all non-survivors will have non-random missing values, and hence would artificially inflate the mean estimates if survivors and non-survivors were analysed together) and will be compared between treatment arms using a repeated measures ANCOVA model with baseline health index/VAS score as covariate, treatment, time and treatment by time interaction as factors, baseline index/VAS score by time interaction, and patient as the experimental unit. Estimated treatment differences (to placebo) along with a 95% confidence interval will be presented for Day 30, 60, 90 and 180. There will be no imputations for missing values.

Page 37 of 80

Furthermore, the QALY, index value and VAS scores will be tabulated treatment arm (including pooled active treatment arms), and the index value and VAS scores will be presented graphically.

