2.2.5 Additional Endpoints

- Hospital-free days up to Day 90
- Hospital length of stay up to Day 90
- Patient residence at Day 30, Day 60, Day 90, and Day 180
- Mean arterial pressure (MAP), until ICU discharge (for a maximum of 7 days)

Page 14 of 80

- Norepinephrine/noradrenaline and other vasopressor doses
- Pharmacokinetic response (in a subset of approximately 200 patients) to be reported separately according to a pre-specified pharmacokinetic analysis plan
- Health economic evaluation to be reported separately according to a pre-specified health economic analytical plan
- Creatinine Clearance
- PaO2/FiO2 ratio (in a subset of 100-350 patients)
- Extravascular Lung Water and Pulmonary Permeability Index (in a subset of 100-350 patients)
- Cardiac output (in a subset of 100-350 patients)
- Cytokines (in a subset of 100-350 patients)
- Angiopoietin 1 and 2 levels (in a subset of 100-350 patients)

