9.2 Primary Endpoint

• Vasopressor- and mechanical ventilator-free days (P&VFDs) up to day 30

This composite endpoint is defined as the number of days (reported to one decimal place (0.0 to 30.0)) from start of treatment with the investigational medicinal product (IMP) [selepressin or placebo] to 30.0 days thereafter during which the patient is: 1) alive; 2) free of treatment with intravenous vasopressors; and 3) free of any invasive mechanical ventilation (see definition below).

Patient Death

By definition, any patient that dies within this 30-day period will be assigned zero P&VFDs, even if there is a period during which the patient is alive and free of both vasopressor treatment and mechanical ventilation.

Definition of "Free of Vasopressors"

Free of vasopressors means less than 60 minutes during any contiguous 24-hour period (regardless of calendar day). If a patient requires periods of vasopressors longer than 60 minutes in total during any 24-hour period, the intervening intervals during which they are free of vasopressors will not be included in the period free of vasopressors in the determination of the number of P&VFDs. Thus, the period free of vasopressors begins at the end of the last use of vasopressors that was either: 1) longer than 60 minutes in duration; or 2) part of greater than 60 minutes of use within a contiguous 24-hour period.

Norepinephrine/noradrenaline, phenylephrine, dopamine, epinephrine/adrenaline, vasopressin, terlipressin, and IMP (i.e. selepressin and placebo) all constitute a vasopressor for the purpose of the primary analysis.

Vasopressor use due to anaesthesia or procedure-induced hypotension during and up to three hours after a surgery or procedure (including bedside) is exempt from this rule (i.e. such use of vasopressors would not affect the calculation of P&VFDs).

Date: 20 Nov 2017 E-Statistical Analysis Plan-17877; Ver.9.0 Supersedes: Ver. 8.0

Page 24 of 80

Definition of "Free of Mechanical Ventilation"

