9.3.1.4 Duration of Mechanical Ventilation up to Day 30

Duration of mechanical ventilation is defined as the cumulative periods (>1 hour) from start of IMP until Day 30, on mechanical ventilation. Mechanical ventilation during - and up to three hours after - surgery / procedure is exempt from this rule.

For patients withdrawn or dying while still on mechanical ventilation, the duration will be based on the data available up until the time of withdrawal or death.

Duration of mechanical ventilation will be analyzed separately for survivors, non-survivors (within the first 30 days) and overall using a zero inflated negative binomial model with time from onset of shock to start of treatment, and norepinephrine/noradrenaline requirement at baseline (μ g/kg/min) as covariates, and treatment and need for ventilation as factors. As duration of ventilation is derived with two decimal points (with values in the range of 0.00, 0.01, ..., 90.00), duration of ventilation

Page 32 of 80

will be transformed (for model stability) to integer values (with values in the range of 0, 1, ..., 9000) by multiplying with 100. Treatment estimates will be back transformed.

In case the model assumptions for duration of ventilation does not hold, the permutation test specified in Section 9.3.1.3 will be used including an analysis of the expected proportion of patients with 0 duration, and estimates of the duration for those with a positive duration.

9.3.1.5 Daily Overall and Individual Organ (Cardiovascular, Respiratory, Renal, Hepatic, Coagulation) Scores using the Modified Sequential Organ Failure Assessment (SOFA) Scores Until ICU Discharge

Last observation carried forward (LOCF) will be used for missing SOFA scores on Days 2-7. No LOCF for Day 1 (as previous value is baseline). Patients dying will be imputed with a worst possible outcome, i.e. a value of 4 for each individual SOFA score.

Daily overall (modified) and individual SOFA scores will be compared between treatment arms up until Day 7 using a repeated measures ANCOVA model with baseline SOFA score as covariate, treatment, time and treatment by time interaction as factors, baseline SOFA score by time interaction, and patient as the experimental unit. The estimated treatment difference (to placebo) with a 95% confidence interval will be presented.

Furthermore, daily overall and individual SOFA scores will be tabulated by treatment arm (including pooled active treatment arms).

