The number of new organ failures and the number of new organ dysfunctions will be compared between treatment arms using a negative binomial model with age, modified SOFA score and norepinephrine/noradrenaline requirement at baseline ($\mu g/kg/min$) as covariates, and gender and treatment as factors. The estimated treatment difference (to placebo) with a 95% confidence interval will be presented. The 95% confidence interval for the difference in proportions between treatment groups will be constructed using the delta method (see Appendix 4 for details).

Furthermore, incidence of any new organ failure and any new organ dysfunction, and the number of new organ failures and new organ dysfunctions will be tabulated by treatment arm (including pooled active treatment arms).

9.3.1.7 Renal Replacement Therapy (RRT)-free Days up to Day 30 (excluding patients on RRT for chronic renal failure at time of randomisation)

RRT-free Days is defined as for the primary endpoint with free of treatment with any form of renal replacement therapy defined as continuous renal replacement therapy, intermittent hemodialysis or peritoneal dialysis.

RRT-free Days will be analyzed excluding patients on RRT for chronic renal failure at time of randomisation.

RRT-free Days up to Day 30 will be analyzed in a similar manner as the primary endpoint, with the van Elteren test stratified by need for ventilation (Yes/No), time from onset of shock to start of treatment (< or \ge 6 hours), norepinephrine/noradrenaline requirement at baseline (< or \ge 30 μ g/min) and baseline creatinine (< or \ge 150 μ mol/L).

9.3.1.8 Incidence of RRT up to Day 30 (counting patients who die as on RRT and excluding patients on RRT for chronic renal failure at time of randomisation)

RRT is defined as any form of renal replacement therapy defined as continuous renal replacement therapy, intermittent hemodialysis or peritoneal dialysis. In order to ensure that any reduction in incidence of RRT is not caused by an increase in mortality, all patients dying within the 30-day period will be counted as on RRT. For patients withdrawn prior to Day 30, incidence of RRT will be based on the data available up until the time of withdrawal.

Page 34 of 80

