Appendix 1 EQ-5D-5L Quality Adjusted Life Year (QALY)

We calculate Quality Adjusted Life Year (QALY) (1), (2) at Day 30 and 180 in three steps:

- (1) A unique EQ-5D-5L health state is defined by combining 1 level from each of the 5 dimensions of EQ-5D-5L. Each health state is referred to in terms of a 5 digit code. For example, state 12345 indicates no problems with mobility, slight problems with washing or dressing, moderate problems with doing usual activities, severe pain or discomfort and extreme anxiety or depression.
- (2) Convert each EQ-5D-5L health state into a single EQ-5D-5L index value. The index values are country specific and we will use the value sets for US and apply these values to all patients in this trial.
- (3) QALY for a patient is then defined to be the area under the curve (AUC) for a Time (with unit of Year) versus index values. AUC will be calculated by the linear trapezoidal method. See below for a schematic presentation where the y-axis is the index value with y_0 , y_1 and y_2 , etc. represent the index values at baseline, Day 30, 60, 90 and 180. The x-axis is Time (in Years) and the t_0 is the start of treatment period, i.e. baseline, and t_1 and t_2 are time of the actual Day 30 and 60, respectively, and so on.

If the index value at baseline is missing then we set QALYs at Day 30 and 180 to missing. No LOCF imputation will be used. However, linear interpolation will be used between data points with missing data in between (e.g. t₀ to t₂, if t₁ is missing).

[figure not shown]

Figure 5: EQ-5D-5L QALY Calculation

Page 52 of 80

Appendix 2 Critical Adverse Events and Classification of Adverse Events Based on Changes in Safety Laboratory Variables

Table 1: Critical Adverse Events

Critical adverse event	MedDRA terms or SMQ used for search				
Potential hypersensitivity reactions	Anaphylactic reaction (SMQ) (Narrow Scope) Angioedema (SMQ) (Narrow Scope)				
Myocardial infarction / ischemia	Ischaemic heart disease (SMQ) (Broad scope)				
Episodes of atrial fibrilation and other cardiac arrythmias	Cardiac Arrhythmias (SMQ) (Broad scope)				
Cerebrovascular accident	Haemorrhagic central nervous system vascular conditions (SMQ) (Broad Scope) Ischaemic central nervous system vascular conditions (SMQ) (Broad Scope) Conditions associated with central nervous system haemorrhages and cerebrovascular accidents (SMQ) (Broad scope)				
Digital ischemia	Peripheral ischaemia Pallor Peripheral coldness				

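### The Section 9.3.3.1 QALY comparison leaves out patients who die, so it cannot show a QALY effect that comes through mortality

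*SAP*

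**What the plan says.** Section 9.3.3.1 analyses the QALY at Day 30 and Day 180 by ANCOVA, with the baseline index as covariate and treatment as factor. It gives this reason for leaving deaths out: "As the QALY is not defined for patients with all remaining values missing, and hence also not defined for those dead". It concludes that "the analyses will automatically only be analyzed for those surviving up until Day 30 and 180 respectively".

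Appendix 1 defines the QALY as the area under the index-against-time curve, by the linear trapezoid, from baseline through the visits at Days 30, 60, 90 and 180. It interpolates between observed points, does not carry values forward, and gives no index value at or after death.

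The only QALY sensitivity analysis concerns the baseline: "imputing the missing baseline scores with the overall mean of the baseline health index". The index value and VAS are modelled separately for survivors and non-survivors at Day 180. The addendum adds nothing on EQ-5D. Section 2.2.5 mentions a separate analysis: "Health economic evaluation to be reported separately according to a pre-specified health economic analytical plan".

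**The concern.** A QALY combines length of life with its quality. Section 9.3.3.1 treats death as if it were missing data, but death is an observed outcome with a known date; Section 9.3.2.3 already plots time to death. Once deaths are removed, everyone compared has approximately the same follow-up (only approximately, because actual visit times are used and the QALY is not rescaled). The survival part of the measure drops out, and what remains is close to average utility among survivors.

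Survival is affected by treatment, so the groups compared are no longer the randomised ones. If one arm keeps alive some patients who would have died in the other, and these are frailer than other survivors, they lower that arm's survivor average. A treatment that adds QALYs could then look as if it costs them, and a harmful one could look favourable. Because index and VAS are also split by survival, no EQ-5D comparison in this SAP covers all patients.

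**Working it through.** The SAP gives no expected QALY, sample size or power for this endpoint, so there is no planned figure to reproduce. The check is an illustration.

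**Inputs from the SAP**
- Placebo mortality 25% (Appendix 8; the horizon is not stated, and it is applied here to Day 180).
- Mortality benefit of 1.5 points (Section 3.2), giving 23.5% on selepressin.
- Horizon T = 180/365.25 = 0.4928 years.

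**Assumptions, not in the SAP**
- Utility 0.7 in patients who survive in either arm.
- Utility u = 0.3, 0.5 or 0.7 in the 1.5% whose survival differs by arm.
- Utility 0 for deaths.

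**Formulas (unadjusted, constant utility)**
- All patients: 0.015 × u × T.
- Survivors only: 0.015 × (u − 0.7)/0.765 × T, where 0.765 is survival on selepressin.

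| u | All patients | Survivors only |
|---|---|---|
| 0.3 | 0.015 × 0.3 × 0.4928 = +0.0022 | 0.015 × (−0.4)/0.765 × 0.4928 = −0.0039 |
| 0.5 | +0.0037 | −0.0019 |
| 0.7 | +0.0052 | 0 |

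The last row is the central result: with equal utility, the survivors-only difference is 0 although the all-patient difference is not. The first two rows show the reversal, which needs the utility gap.

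**With the Appendix 1 trapezoid.** Taking an assumed baseline index of 0.8 and no QALYs for deaths, u = 0.3 gives −0.0035 in survivors and +0.0025 in all patients.

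**With baseline adjustment as well.** A simulation with the SAP's ANCOVA assumed mean pre-admission index 0.8, 0.6 and 0.65 (survive in either arm, survival differs, die in either arm), SD 0.2, correlation 0.5, and 80% of deaths before Day 30. For u = 0.3, 0.5 and 0.7 it gave about −0.0025, −0.0008 and +0.0009 in survivors, against +0.0024, +0.0033 and +0.0045 in all patients. Adjustment shrinks the reversal and removes it when there is no utility gap.

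**Precision.** The number of patients at the futility stop is not in the SAP. At 800 patients (the Part 1 maximum, split 267/533) with an assumed survivor utility SD of 0.2 to 0.3, the standard error is 0.013 to 0.015 for all patients and 0.009 to 0.013 for survivors. Every difference above is well below its standard error.

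**Two checks on the repair**
- *Dropping living non-responders while keeping deaths.* If 20% of living patients lack a QALY, the placebo death share becomes 0.25/(0.25 + 0.75 × 0.8) = 29.4% instead of 25%. With 20% missing on placebo, 25% on selepressin and no mortality effect, the false difference is [0.5625/0.8125 − 0.6/0.85] × 0.7 × 0.4928 = −0.0047 QALY.
- *Trapezoid from the pre-admission baseline.* A patient with baseline 0.8 who dies on Day 20 is credited 0.8 × 20/2/365.25 = 0.022 QALY for time spent in septic shock. That is about four to ten times the all-patient differences in the table.

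**The case against.** The strongest reply is that this is a quality-of-life endpoint, not the trial's health economics. The restriction is stated openly, mortality is tested at Days 30, 90 and 180, and the separate economic plan is a natural home for a QALY that includes deaths. All of this is fair. It limits the point to what this SAP reports, and a reader should not infer that the trial has no QALY analysis with deaths included. It does not change what the Section 9.3.3.1 estimate can show.

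A second reply is that Appendix 1 gives no index at death, so the area cannot be computed as written, and that 0 from death is an added convention. That is correct as to the text. The convention follows from a QALY being time lived weighted by utility, and the SAP's reasoning from missing values does not supply an alternative.

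A reader might infer a breach of the rule that efficacy is analysed in the full analysis set, or a departure from settled SAP practice. The document does not support that. It scores deaths for some endpoints: "any patient that dies within this 30-day period will be assigned zero P&VFDs"; for SOFA, "Patients dying will be imputed with a worst possible outcome"; and for RRT incidence, with the stated purpose "In order to ensure that any reduction in incidence of RRT is not caused by an increase in mortality". But it sets deaths to missing for daily fluid balance (9.3.4.1) and vasopressor doses (9.4.5). Handling is chosen endpoint by endpoint, and the case here rests on what a QALY is.

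The last reply is that the numbers are small and rest on assumed utilities, and that the repaired analysis would be imprecise too. This stands. Nor should a reader infer that a reversal is likely: it depends on a utility gap that the SAP does not give.

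**Conclusion.** The point holds for Section 9.3.3.1. The stated reason for excluding deaths does not follow from the QALY being an area over time, and the survivors-only comparison cannot show a gain or loss that comes through mortality. That conclusion needs no assumed utilities beyond equal utility in survivors of both arms, in which case the difference is about 0.

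A wrong sign is possible but conditional. In the illustration it is −0.0039 against +0.0022 QALY unadjusted, and smaller after baseline adjustment. These values rest on utilities of 0.3 and 0.7 and on applying 25% mortality to Day 180.

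The consequence is a secondary estimate that is easily misread. A reader might infer a risk to a label claim, but the QALY is outside the Hochberg family and the key mortality endpoint is tested on its own. The change is worth making without being critical to the trial's conclusions.

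**What to change.** - Make the main QALY comparison at Day 30 and Day 180 a full-analysis-set analysis with index 0 from the date of death. Use the same baseline-adjusted ANCOVA with a bootstrap confidence interval.
- Impute a missing baseline by the SAP's existing overall-mean rule. Impute missing later values of living patients within arm, from baseline and their observed values, and state the imputation model and how it is combined with the bootstrap. Do not keep deaths while dropping living non-responders; disclosing the missing fraction would not remove that bias.
- Fix in advance the rule for utility between start of treatment and an early death. Add a sensitivity analysis that credits 0 for deaths before the first post-baseline visit, because the last available index is then the pre-admission baseline.
- Keep the survivors-only QALY as supportive, labelled as conditional on survival.

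The cost is SAP wording plus some derivation and imputation work. Time to death is already analysed, so no new data are needed.

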9.3.4 Fluid Balance

9.3.4.1 Daily and Cumulative Fluid Balance Until ICU Discharge (for a Maximum of 7 Days)

Fluid overload is defined as fluid balance volume (L) as a percentage of baseline weight. E.g. if a patient weighs 90 kg at baseline and has a fluid balance of 9 liters, fluid overload is then 100% * 9L / 90 kg = 10%.

Fluid balance (as a rate of time) and cumulative fluid balance (total volume) will be presented both unadjusted and adjusted for weight.

Baseline fluid balance (as a rate of time) and baseline fluid balance volume (mL) will be based on the time from onset of sepsis induced hypotension to start of IMP.

All analyses will be presented for 'all patients' and for 'patients in ICU throughout Day 0-7'.

Fluid balance, cumulative fluid balance, fluid overload and cumulative fluid overload will all be compared between treatment arms using a repeated measures ANCOVA model with baseline (baseline fluid balance volume (mL) or baseline fluid overload) as covariate, treatment, time and treatment by time interaction as factors, baseline score by time interaction, and patient as the experimental unit. Estimated treatment differences (to placebo) along with a 95% confidence interval will be presented.

Fluid overload and balance will be based on a sectioning of the intervals between the actual sampling time points on baseline, Day 1, 2, etc., in order to be able to make 24 hour intervals from start of IMP.. For Days 1, 2, etc. sampling time points will be every 24 hours from start of IMP. Patients withdrawn or dead will be set to missing.

Endpoints (absolute values and change from baseline) will be tabulated by treatment arm (including pooled active treatment arms), and presented graphically.

Furthermore, in order to assess all patients at Day 3 and 7 (regardless of mortality), the composite endpoint 'critical edema-free survival' will be derived at both Day 3 and 7.

A patient will be categorised as being critically edema-free and alive at Day 3 (or 7 respectively) if:

- fluid overload < 10% at Day 3, or
- patient is discharged from ICU and emergency department prior to Day 3 with a fluid overload < 10% at day of discharge (or previous day if discharged before fluid balance measurement), and patient is alive at Day 3.

The patient will be categorised as not being critically edema free or dead if:

• fluid overload $\geq 10\%$ at Day 3, or

Date: 20 Nov 2017 E-Statistical Analysis Plan-17877; Ver.9.0

Supersedes: Ver. 8.0 Page 38 of 80

• patient is discharged from ICU and emergency department prior to Day 3 with a fluid overload ≥ 10% at day of discharge (or previous day if discharged before fluid balance measurement), or

• patient is dead on Day 3 (prior to fluid balance measurement)

Patients withdrawn at the given time point will be set to missing (less than 20 patients total in the trial are expected to be withdrawn prior to Day 7). The endpoints will be analysed using a logistic regression model with baseline fluid overload as a covariate and treatment arm as a factor, presenting odds ratios with 95% confidence intervals.

9.3.4.2 Daily and Cumulative Urinary Output Until ICU Discharge (for a Maximum of 7 Days)

Urinary output and cumulative urinary output (absolute values) will all be will be compared between treatment arms using a repeated measures ANCOVA model with baseline urinary output volume (mL) as covariate, treatment, time and treatment by time interaction as factors, baseline score by time interaction, and patient as the experimental unit. Estimated treatment differences (to placebo) along with a 95% confidence interval will be presented.

Urinary output and cumulative urinary output will be presented both unadjusted and adjusted for weight.

All analyses will be presented for 'all patients' and for 'patients in ICU throughout Day 0-7'.

Urinary output will be derived in the same manner as fluid balance.

Endpoints (absolute values and change from baseline) will be tabulated by treatment arm (including pooled active treatment arms), and presented graphically.

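### Critical edema-free survival is scored on fluid overload, which the SAP lists apart from cumulative fluid overload, so read literally the 10% limit applies to one day's balance

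*SAP*

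**What the plan says.** All of the relevant text is in SAP section 9.3.4.1.

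- Definition: "Fluid overload is defined as fluid balance volume (L) as a percentage of baseline weight". The worked example is 9 L in a 90 kg patient, giving 10%. Neither names a time window.
- Variables analysed: "Fluid balance, cumulative fluid balance, fluid overload and cumulative fluid overload will all be compared between treatment arms". These are four distinct quantities.
- Derivation: fluid overload and balance rest on a sectioning of the sampling intervals, "in order to be able to make 24 hour intervals from start of IMP".
- Composite, responder side: "fluid overload < 10% at Day 3, or" for patients still under observation, and "fluid overload < 10% at day of discharge" (or the previous day) for those discharged earlier and alive at Day 3. Day 7 follows the same rule.
- Composite, failure side: overload of at least 10% at Day 3, death, or "patient is discharged from ICU and emergency department prior to Day 3 with a fluid overload ≥ 10% at day of discharge".
- Two sentences bear on the intended meaning. The first distinguishes "Fluid balance (as a rate of time) and cumulative fluid balance (total volume". The second says that "baseline fluid balance volume (mL) will be based on the time from onset of sepsis induced hypotension to start of IMP".

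The composite is analysed by logistic regression with baseline fluid overload as covariate. The SAP addendum does not return to it.

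**The concern.** Edema reflects fluid accumulated over days. The section has a name for the accumulated quantity, *cumulative fluid overload*, but no criterion of the composite uses it. A programmer who follows the text would take the 24-hour value, because the SAP lists the cumulative one separately.

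On that reading a heavily overloaded patient counts as edema-free unless the balance of the one day examined reaches a tenth of body weight. The composite was added so that all patients could be assessed at Days 3 and 7 regardless of mortality. If its edema part is rarely triggered, the odds ratio mainly reflects early survival while carrying an edema label. The same patient can also be a responder or a failure depending on which of the SAP's two variables is used, and nothing in the text settles that choice before the data are seen.

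**Working it through.** **The SAP's own figure.** 100 × 9 L / 90 kg = 10.0%. It reproduces.

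**One patient, two variables** (illustrative balances, 90 kg). Daily net balances of +5, +3 and +2 L give daily values of 5/90 = 5.6%, 3/90 = 3.3% and 2/90 = 2.2%. The cumulative value at Day 3 is 10/90 = 11.1%. The patient is edema-free on the 24-hour reading and a failure on the cumulative one.

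**The limit in litres.** Limit = 0.10 × weight. For assumed weights of 50 to 120 kg it is 5 to 12 L. On the 24-hour reading that is the net balance needed within one day. On the cumulative reading the average needed is limit/3 = 1.67 to 4.0 L/day to Day 3, or limit/7 = 0.71 to 1.71 L/day to Day 7. At 80 kg the figures are 8 L in one day, 2.67 L/day and 1.14 L/day.

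**How often the limit is reached.** The SAP gives no distribution of daily balance and no Day 3 or Day 7 mortality, so everything below is assumption. Take an 80 kg patient (8 L) and a normal daily balance with mean m, SD s and between-day correlation ρ:

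- one interval: P = 1 − Φ((8 − m)/s)
- sum over k days: P = 1 − Φ((8 − km)/(s√(k + k(k−1)ρ)))
- share of failures due to edema rather than death: (1 − d)P / ((1 − d)P + d), with assumed mortality d of 5% or 10% by Day 3

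Results for ρ = 0:

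| m / s (L) | One interval | Cumulative to Day 3 | Cumulative to Day 7 | Edema share of Day 3 failures, one interval (d = 5% / 10%) | Edema share, cumulative to Day 3 (d = 5% / 10%) |
|---|---|---|---|---|---|
| 0 / 1.5 | <0.001% | 0.1% | 2.2% | <0.1% / <0.1% | 1.9% / 0.9% |
| 0.5 / 1.5 | <0.001% | 0.6% | 12.8% | <0.1% / <0.1% | 10.5% / 5.3% |
| 1 / 2 | 0.02% | 7.4% | 42.5% | 0.4% / 0.2% | 58.6% / 40.1% |
| 1 / 3 | 1.0% | 16.8% | 45.0% | 15.7% / 8.1% | 76.1% / 60.2% |
| 2 / 3 | 2.3% | 35.0% | 77.5% | 30.2% / 17.0% | 86.9% / 75.9% |
| 2 / 4 | 6.7% | 38.6% | 71.5% | 55.9% / 37.5% | 88.0% / 77.7% |

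With ρ = 0.3 the one-interval column is unchanged. The cumulative Day 3 values become 0.7% to 41.0%, and the Day 7 values 11.4% to 67.4%.

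**The origin matters too.** Suppose the pre-IMP volume is added, with an assumed mean of 3 L and SD of 2.5 L, independent of the later balance. The 1 / 2 case with ρ = 0 then moves from 7.4% to 1 − Φ((8 − 3 − 3)/√(12 + 6.25)) = 32.0% at Day 3. The SAP does not say whether that volume counts towards the 10%.

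**The case against.** The strongest reply is that a cumulative value was meant all along. Fluid overload is defined on a volume, and the SAP describes fluid balance as a rate and cumulative balance as the total volume. The worked example lands exactly on the composite's threshold and names no 24-hour window. The sentence on sectioning may only describe how irregular sampling times are aligned to a common grid, which cumulative values need as well.

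This stands as evidence of intent: the 24-hour reading is the literal one, not the only one. It does not clear the text. If fluid overload were already cumulative, listing cumulative fluid overload beside it would be redundant. The word volume does not settle the window either, because the section also uses it for the pre-IMP period. If the intent was cumulative, the composite names the wrong variable.

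A reader might go further and infer that the 10% limit is almost never met and that the composite collapses into survival. The SAP does not support that. It holds no balance distribution and no early mortality. At the upper end of the assumed range, edema still makes up 38% to 56% of Day 3 failures on the 24-hour reading. At the lower end (mean 0 L, SD 1.5 L, ρ = 0) it makes up only 1% to 2% on the cumulative reading too, so naming the cumulative variable would change little there.

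It is also fair to say that an effect on fluid accumulation is assessed elsewhere. Cumulative fluid balance and cumulative fluid overload each have a repeated-measures analysis in the same section.

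**Conclusion.** The point holds as a defect of definition. As written, every edema criterion rests on a variable that the SAP distinguishes from the cumulative one and ties to 24-hour intervals. A patient who has accumulated more than 10% of body weight can therefore be scored edema-free. That much follows from the text and the 90 kg arithmetic alone.

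That the edema part would add little beyond survival is conditional. It holds in much of the assumed range (daily mean 0 to 2 L, SD 1.5 to 4 L, 80 kg, Day 3 mortality 5% to 10%), but not throughout.

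The reach is limited. The composite is a supportive derivation under fluid balance and is not named in the endpoint list of section 2.2. It lies outside the three key secondary endpoints in the Hochberg procedure of section 9.3. No primary or key secondary conclusion depends on it. It is still worth correcting, because it determines how individual patients are classified in an analysis that reports odds ratios with confidence intervals.

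**What to change.** In section 9.3.4.1, replace *fluid overload* with *cumulative fluid overload* in every criterion of critical edema-free survival: Day 3, Day 7 and discharge, on both the responder and the failure side. State the origin of the accumulation in the same place. One option is from start of IMP, with the pre-IMP volume kept as the baseline covariate already planned. Otherwise, say explicitly that the pre-IMP volume is included in the Day 3 and Day 7 values.

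The cost is a few words in the SAP or its addendum. The cumulative variable is already needed for the repeated-measures analysis, so no new data or derivation is required. The change should be fixed before unblinding so that the choice cannot depend on the results.
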